This is a multicenter observational study to develop predictive models for sepsis and necrotizing enterocolitis in preterm infants, using clinical, laboratory, and bedside monitor data.

- No interventions are involved.
- Clinical, laboratory, and imaging data will be collected from the medical record.
- Vital sign data will be collected from the bedside monitors.
- Machine learning will be used to develop, test, and validate predictive algorithms

SYNOPSIS

Title: Predictive Modeling for sepsis and necrotizing enterocolitis in preterm infants
Investigators: [name].; [name].
Planned Study Initiation: November 2018
Study Duration: 10 years
Length of subject participation: Study data are collected from birth until NICU discharge. Neurodevelopmental follow-up data will be collected until age 2.
Objective: To test the hypothesis that validated algorithms combining cardiorespiratory metrics from NICU bedside monitors with clinical, demographic and laboratory variables can provide early warning for sepsis and NEC in VLBW infants in the NICU.
Outcomes: Primary: 
• Late-onset (>3d of age) sepsis• Other late-onset infections• Necrotizing enterocolitis Secondary: 
• Mortality• Days on mechanical ventilation• Preterm morbidities including but not limited to brain injury, retinopathy, acute kidney injury, and bronchopulmonary dysplasia• Days on antibiotics• Length of NICU stay• Neurodevelopmental outcomes at routine NICU follow-up visits

IRB # 21237: Predictive Modeling for Sepsis and Necrotizing Enterocolitis in Preterm Infants

NICHD: RO1 HD072071:

PI: [name],

Version dated March 10, 2025

Methodology: Observational study with data collection from electronic health record
Total Number of infants planned: 8500
Inclusion criteria:

 • Birthweight <1500 grams
Exclusion criteria:

 • None
Investigational intervention: None (data collection only)
Other study intervention(s): None
Statistical methods: Descriptive statistics, logistic regression, decision tree, neural network, deep learning and others will be utilized.
Efficacy: Algorithms for sepsis and NEC risk will be developed and externally validated and cross-validated.

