- The combined efforts of clinicians, mathematicians and engineers can lead to effective new monitoring strategies that allow early diagnosis of otherwise invisible clinical deterioration.
- Adding clinical, demographic, and laboratory data to bedside monitor cardiorespiratory data will improve prediction and early detection of sepsis and NEC over any of these data alone.
- Improved analytics will favorably impact patient outcomes by assisting clinicians in decisions about initiation of antibiotics and other therapies early in the course of illness.

IRB # 21237: Predictive Modeling for Sepsis and Necrotizing Enterocolitis in Preterm Infants

NICHD: RO1 HD072071:

PI: [name],

Version dated March 10, 2025

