5. STATISTICAL CONSIDERATIONS

Statistical Methods

Clinical, demographic, and cardiorespiratory parameters are combined using multivariate statistical methods, such as logistic regression, k nearest neighbor analysis, random forests, neural nets, and other techniques(12)(13). The period of interest is the 24 hours prior to the event. Thus the output of the model is the probability of an event in the next day. We divide by the average probability of the event, and present the clinician with the fold-increase in risk of an upcoming event. We will have a development/test cohort and validation cohort both within and between centers to account for differences in clinical practices that may impact vital sign patterns.

Study Size Considerations

We anticipate enrolling at least 1667 VLBW infants per site over a 4-year period. With incidence of late-onset sepsis and NEC being approximately 15% and 7% respectively, we anticipate having about 200 episodes of culture-positive sepsis and 100 episodes of NEC with bedside monitor data available for analysis. Generally, 50 events allow for a predictive model with 5 predictive variables and (based on our experience with bootstrapping) 95% CI of 0.3 around the ROC area, so we will have sufficient numbers of infants with events to develop and validate models.

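### Do about 100 NEC episodes, once divided between development and validation, undercut the plan's claim that numbers are sufficient?

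*Combined protocol and SAP*

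**What the plan says.** Study Size Considerations (section 5) starts from recruitment: "We anticipate enrolling at least 1667 VLBW infants per site over a 4-year period". It then applies event rates: "With incidence of late-onset sepsis and NEC being approximately 15% and 7% respectively". From these it states that "we anticipate having about 200 episodes of culture-positive sepsis and 100 episodes of NEC with bedside monitor data available for analysis", without saying whether the counts are per site or for the study.

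The justification is a rule of thumb, "Generally, 50 events allow for a predictive model with 5 predictive variables", joined to a precision figure credited to the group's bootstrapping experience: "95% CI of 0.3 around the ROC area, so we will have sufficient numbers of infants with events to develop and validate models". It is not said whether 0.3 is a full width or a plus/minus, and no target width is given.

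Three other places bear on the point:

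- Statistical Methods (section 5): "We will have a development/test cohort and validation cohort both within and between centers". No split fraction is stated.
- Synopsis: "Total Number of infants planned: 8500". Its efficacy entry says the algorithms will be cross-validated as well as externally validated.
- Specific Aims (section 2.2): the last aim is external validation at the other participating NICUs.

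**The concern.** The study-size paragraph never divides its event counts between the cohorts that the preceding paragraph promises. If half of 100 NEC episodes go to validation, 50 remain, exactly the count to which the plan attaches an interval of 0.3. Around an assumed AUC of 0.75 that is 0.60 to 0.90 as a full width. As plus or minus 0.3 it is 0.45 to 1.00 (capped), which includes chance. Neither would separate a weak algorithm from a strong one.

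The 0.3 is also about twice what a standard formula gives for 50 events. So either NEC validation is very imprecise, or the only precision figure in the section is wrong.

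NEC is a primary outcome, and the rationale in section 1 expects that combining data sources "will improve prediction and early detection of sepsis and NEC over any of these data alone". If validation were this loose, the study could finish without knowing whether its NEC model works or whether the added data helped.

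**Working it through.** **1. Event counts.** Inputs are from section 5 and the Synopsis.

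- One site: 1667 × 0.15 = 250 sepsis and 1667 × 0.07 = 117 NEC. The stated 200 and 100 are 80% and 86% of these.
- Whole study: 8500 × 0.15 = 1275 and 8500 × 0.07 = 595. The stated counts are 16% and 17% of these.

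The stated counts are not reproduced exactly on either reading, but per site is far closer. The 80% should not be taken as a monitor-data yield: it compares culture-positive episodes having monitor data with all late-onset sepsis, so it also mixes culture positivity and episodes versus infants.

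Per site, the study-level figures are 8500 × 200/1667 = 1,020 sepsis and 8500 × 100/1667 = 510 NEC. The number of sites is not stated; 8500/1667 = 5.1 suggests about five.

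**2. The plan's own rule.** Fifty events for 5 variables is 10 events per variable. An even split of 100 gives 50 for development and 50 for validation, so the rule is met.

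**3. The plan's own precision, scaled.** Take 0.3 as a full width and width = 0.3 × √(50/events). The square-root scaling is an assumption.

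| NEC validation set | Events | Width |
|---|---|---|
| Half of 100 | 50 | 0.30 |
| One third of 100 | 33 | 0.37 |
| One fifth of 100 | 20 | 0.47 |
| All 100, cross-validated, or one other whole site | 100 | 0.21 |
| Half of the pooled 510 | 255 | 0.13 |
| Four other sites | 400 | 0.11 |

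The first three rows describe the whole study only if 100 is a study total. Otherwise they describe a single center with a held-out split. The last two rows need the per-site reading. For sepsis, half of 200 is 100 events, width 0.21.

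**4. Is 0.3 reproducible?** The Hanley-McNeil variance is [A(1−A) + (n1−1)(q1−A²) + (n0−1)(q2−A²)]/(n1·n0), with q1 = A/(2−A) and q2 = 2A²/(1+A). Use A = 0.75, n1 = 50 and n0 = 833 − 50 = 783 (half of 1667, less the events):

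- q1 = 0.600, q2 = 0.643, A² = 0.5625
- variance = (0.1875 + 49 × 0.0375 + 782 × 0.0804)/(50 × 783) = 0.00166, so SE = 0.0407
- full width = 2 × 1.96 × 0.0407 = 0.16

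Over AUC 0.70 to 0.90 the width runs from 0.17 to 0.12. With one control per event it is at most about 0.22 (AUC 0.60). The formula does not reproduce 0.3, but it treats the model as fixed and each infant as one independent observation.

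**5. Comparing two models in the same infants.** Starting from a half-width of 0.15, the half-width of the AUC difference is 0.15 × √(2(1−r)): 0.15 at r = 0.5 and 0.07 at r = 0.9 (correlations assumed).

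**The case for a change.** The strongest case for a change is that on either reading at least one promised NEC validation sits at the plan's own 0.3: the whole study if the counts are totals, the within-center cohort if they are per site. The paragraph moves straight from that figure to sufficiency with no target width, and the remedy would be only wording and one recalculation.

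Part of this stands. The unit of the counts, the meaning of 0.3, the split and the target are all absent, and a reader cannot confirm sufficiency from the text.

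The rest does not carry. The 50 comes from an even split that the plan does not state. It also supposes that a within-center assessment uses only a held-out half, although the Synopsis promises cross-validation. On the likelier per-site reading, external validation draws on whole other sites.

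Nor is it a choice between an imprecise study and a misstated figure. The 0.3 is tied to a 5-variable model and to bootstrapping, so it may include the variability of fitting. The models also predict risk over the coming day, so one infant contributes repeated observations. Either could make it wider than Hanley-McNeil without being wrong, though the text does not say which applies. If Hanley-McNeil is the better guide for validation, 50 events give about 0.16 and the alarm over 0.60 to 0.90 falls away.

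The paired-difference argument rests on a rationale statement. The hypothesis in section 2.1 is that the algorithms can give early warning, and no formal test of AUC differences is planned.

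**Conclusion.** The concern does not call for a change. Its arithmetic is right, but it shows only that sufficiency is undemonstrated. With no target width in the plan, calling 0.3 too wide is a judgement, not a missed figure.

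The weak spot is a held-out NEC validation set of about 50 episodes. It affects the whole study only if 100 is a study total, which would be 17% of the 595 expected, and the split is even. Otherwise it is confined to one center assessed without cross-validation. Pooled or external NEC validation would then have widths of about 0.21 to 0.11 on the plan's own figure. These sizes assume square-root scaling, about five sites, one episode per affected infant and 0.3 as a full width.

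The missing detail is of a kind analysts fill in as they work. The sizing paragraph sets no stopping rule, test or threshold. The study takes all infants under 1500 g with no exclusions, so rewording would add no events and alter no analysis. The AUC interval in each validation cohort will come from the data actually collected, and it will show directly how well NEC prediction has been established.

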6. STUDY MANAGEMENT

Institutional Review Board (IRB) Approval and Consent

This is a purely observational study. Bedside monitor data are currently collected and stored at all sites. Routine clinical data are annotated in the electronic health record. For purposes of this study, waiver of consent is appropriate since there are no interventions, data are considered de-identified under the Privacy Rule since they have only the limited HIPAA identifiers of date and Study ID , (Limited Data Set) and securely stored, and requiring consent would impact the study results since the consented population would be smaller and may differ from the entire VLBW cohort in ways that could impact the validity of the sepsis and NEC algorithms we develop. Data will be collected either prospectively or retrospectively.

7. Study Records and Record Retention

IRB # 21237: Predictive Modeling for Sepsis and Necrotizing Enterocolitis in Preterm Infants

NICHD: RO1 HD072071:

PI: [name],

Version dated March 10, 2025

Study documentation includes all electronic case report forms in REDCap, source documentation, Sponsor-Investigator correspondence, regulatory documents (e.g., protocol and amendments, IRB correspondence and approval) and the like.

Source documentation will be captured in electronic format and include information from patient's electronic medical records and / or data obtained from various bedside vitals monitoring equipment e.g., using BedMasterEx software (Excel Medical), Philips Data Warehouse Connect and include all recordings of observations or notations of clinical activities and all reports and records necessary for the evaluation and reconstruction of the clinical research study.

Study documentation will be kept on file for the length of time that is required by each participating sites IRB.

IRB # 21237: Predictive Modeling for Sepsis and Necrotizing Enterocolitis in Preterm Infants

NICHD: RO1 HD072071:

PI: [name],

Version dated March 10, 2025

